Given this increased uptake of IBR, it is important to study the patient's quality of life after mastectomy and reconstruction. When compared to mastectomy alone, current research shows improved quality of life in patients who opt to receive reconstruction[4]. Women opting for reconstruction reported positive effects on their self-esteem, body image, sexuality and psychological health.

Currently there are two well established methods of breast reconstruction after mastectomy: autologous 'flap' reconstruction or implant reconstruction. Whilst autologous reconstruction utilises tissue transfer from the patient themselves, implant reconstruction uses a silicone implant device or a saline tissue expander to re-create the breast mound. Implant reconstruction is the commonest form of breast reconstruction and in Leeds Teaching Hospitals NHS Trust (LTHT), 60% of patients receiving IBR opt for implant based reconstruction. The breast surgery unit at LTHT is a national oncoplastic fellowship centre and perform around 100 IBR of all types per year (personal communication and analysis; author BK).

Traditionally immediate implant based reconstructions were not technically possible as implant size required to recreate breast shape was usually too large and raising pectoralis major and serratus anterior muscle was insufficient to cover and stabilise the implant position[5]. Therefore, smaller expanders were commonly placed under both muscles and gradually inflated. This was then later exchanged to an implant. The aesthetic outcome from such procedures was sub-optimal with increased risk of pain and implant malposition.

More recently, acellular dermal matrices [6] has led to an improvement in implant based breast reconstruction. Acellular dermal matrix is sutured to the lower part of pectoralis muscle that is raised. This enables full coverage and stabilises the implant and therefore avoids the need for raising the serratus anterior muscle or routine use of expanders. As a result, this reduces the number of surgeries the patient requires, as well as improve aesthetic outcome. This technique is defined as sub-pectoral implant based breast reconstruction. It has been adopted widely [7] and has become established as standard practice.

In the last 5 years, surgical techniques and technologies have advanced further to enable the implant to be placed above the pectoral muscle. This avoids the need to raise the pectoral muscle and therefore has advantages in reducing post-operative pain and length of the operating time. This has been made possible with larger acellular dermal matrices that are able to stabilise implant position without needing to raise the pectoral muscle to cover the implant device. This technique is defined as pre-pectoral implant based breast reconstruction[8] and has been adopted widely in UK given the perceived advantages for the patient. There is currently a national study [9] that is examining patient outcome in pre-pectoral implant based breast reconstruction. Figure 1 clearly demonstrates the difference between pre- and sub-pectoral implant reconstruction.

[figure not shown]

Figure 1. Pre- versus sub-pectoral breast reconstruction [10]

Both surgical techniques have proven safety for the patient in demonstrating low complication rates such as implant loss rate due to infection. There are potential advantages as well as disadvantages for each surgical technique as demonstrated by the table 1.

Sub-pectoral	Pre-pectoral
Raising the pectoral muscle can result in excess upper pole fullness of the reconstructed breast.	More predictable aesthetic result as the pectoral muscle is not raised.
Animation deformity, which is defined as visible twitching of the pectoral muscle (under the skin) with certain arm or shoulder movements. Patients may find this unsightly.	No animation deformity.
Potentially greater pain due to partial division of the pectoral muscle resulting in slower recovery to normal function.	Potentially less pain and therefore shorter hospital stay and quicker recovery to normal function.
Additional tissue coverage over the implant resulting in less likelihood of implant palpability, rippling, or capsular contracture.	Thin tissue coverage over the implant. This may increase the risk of rippling which may be treated with further revisional surgery (e.g. lipomodelling to improve tissue coverage over the implant).

Table 1. Potential advantages and disadvantages of pre- vs. sub-pectoral implant based breast reconstruction.

Given the equipoise and proven safety of both surgical techniques, eligible patients are counselled about their surgical options when opting for implant based breast reconstruction. Implant based reconstruction includes a fixed volume silicone implant device as well as an expander device which has an outer silicone shell with an internal saline chamber which can be inflated gradually once the surgical wound has healed. Expanders can be used for both pre- and sub-pectoral reconstruction and is used in cases where there are potentially higher wound healing risks (e.g. patients with smoking history). This is fully discussed between the surgeon and the patient as part of a standard informed consent.

At LTHT, we are able to offer patients both pre- and sub-pectoral implant based reconstruction. The current practice shows that equal proportion of patients opt for pre- versus sub-pectoral implant based IBR (BK: personal communication and preliminary data). However, it is unclear how much of this decision making is influenced by the patient or the surgeon. There is no current research of national guideline suggesting recommendation of one surgical technique versus the other.

Therefore, it becomes even more important to examine and compare patient reported outcome measures (PROMs) in both patient groups. This is an important research question as if PROMs are significantly higher in one patient group versus the other, this has significant implications for future patients when counselled with regards to their surgical options. Decision making for breast reconstruction is complex for the patient and the healthcare professionals involved. Therefore, further research such as this study is required to aid this process.

BREAST-Q is a validated questionnaire specific for breast patients undergoing reconstruction [11-13]. It is able to assess multiple pertinent PROMs including the patient's expectation of breast reconstruction, the level of pain, physical function after surgery, satisfaction with shape of the reconstruction, and satisfaction with the treating medical team and the level of information provided. Importantly, it has questions specific to implant based breast reconstruction and has specific questions relating to the potential issue of animation deformity [14]. It is also validated for use at multiple time points after surgery (including longer term PROMs at 12 months). Therefore, assessing PROMs using the BREAST-Q in patients undergoing pre- or sub-pectoral implant based IBR at the Leeds Breast Unit, a high volume reconstructive surgery centre, provides an ideal setting to answer this important research question.

4. Objectives and Outcome Measures

Does the difference in the surgical technique for immediate implant breast reconstruction (pre- versus sub-pectoral) influence patient perceived outcomes?

Aims:

The current lack of research evidence and guidelines on the topic signifies that the type of operation undertaken usually comes down to surgeon or patient preference. By completing this project we aim to provide better:

- Patients with curated information regarding short and longer term post-surgical patient reported outcomes.
- Healthcare professionals with a more extensive understanding of the advantages and limitations of both types of surgery from the patient's perspective.

This will equip the patient and the healthcare professional to make more informed decisions regarding the optimal surgical technique.

Objectives:

- Compare aesthetic outcome of pre- and sub-pectoral reconstructions using Patient Reported Outcome Measures (PROMs)
- Compare potential difference in pain between pre- and sub-pectoral reconstructions as reported by PROMs
- Compare potential difference in functionality between pre- and sub-pectoral reconstructions using PROMs

Outcome Measures:

We will collect PROMS on a prospective cohort of patients undergoing immediate implant based reconstruction after mastectomy for cancer or for risk reduction. The Association of Breast Surgery (ABS) guidelines for oncoplastic breast surgery [15] states that patients undergoing breast reconstruction should have PROMs data collected on a routine basis. We will utilise the BREAST-Q questionnaire (BREAST-Q, 2017), which is a validated PROMs survey that has been published widely.

5. Trial Design**5.1 Research Design**

A prospective non-randomised longitudinal cohort study with data collection for patients undergoing mastectomy with immediate implant based reconstruction surgery for early breast cancer or risk reduction using repeated measures and mixed methods.

5.2 Study Measures

a) Clinical Outcomes and process of care measures

e.g. anaesthetic blocks used, number of hospital contacts, unplanned admissions, clinic appointments, phone calls with hospital staff, medications prescribed and taken, any changes to treatment plan. Details will be obtained via the individual electronic patient records.

b) Patient Reported outcomes

PROs using validated questionnaires

The BREAST-Q utilises PROMs to evaluate outcomes for various types of breast surgeries. Two of its 'modules' are relevant to this study; 'Reconstruction' and 'Reconstruction Expectations'. Each module contains multiple independently scored 'scales' with overarching themes of psychosocial and physical quality of life. To establish a baseline pre-operatively, we will use the 'Reconstruction Expectations' module. To explore the change in PROMs over time, the 'Reconstruction' module will be given to patients post-operatively (BREAST-Q, 2017). The main strength of using BREAST-Q is that it allows for comparison to other work in the same field of research. Furthermore, the outcome of the study could aid in designing and setting up of future multi-centre studies.

The questionnaires will be collected at four time points; pre-surgery, 2 weeks post-surgery and at 3 and 12 months post-surgery. This is in line with current clinical follow up for patients undergoing implant based reconstruction in Leeds. Therefore, patients will not require any additional clinical visits. The PROM scores may also be influenced by their surgical outcome (e.g. complication after reconstructive surgery). Therefore, routine clinical data regarding the patient's treatment outcome (e.g. any return to theatre or re-admission) will be collected alongside sociodemographic, relevant medical history data and the questionnaire.

5.3 Study Duration

Patients will be a participant in the study for approximately thirteen months. Thirteen months following surgery is completion of the patient's involvement in the study.

5.4 Findings

The overall findings will determine the feasibility of using this approach to support the care of patients undergoing immediate implant based reconstructive surgery for breast cancer or risk reduction. All data and opinions will inform the future development of information which aims to improve patient choice, experience and outcomes.

6.0 Participant Identification

6.1 Trial Participants

The sample of patients will include all prospective patients who undergo immediate implant based breast reconstruction in the Leeds Breast Unit between August 2020 and September 2021.

6.2 Inclusion criteria

- Female age \geq 18 years
- Skin or nipple sparing mastectomy with immediate implant based reconstruction for cancer or for risk reduction (e.g. BRCA mutation)
- Unilateral or bilateral mastectomy
- Implant or expander based immediate reconstruction
- Able to read and understand questionnaire in English

6.3 Exclusion criteria

- Male or transgender
- Skin or nipple sparing mastectomy alone with no reconstruction
- Delayed reconstruction
- Autologous reconstruction
- Cognitive impairment or inability to provide informed consent

6.4 Participants in the local service evaluation

Patients who have already completed the questionnaires through their participation in a local service evaluation, will also be approached to ask to participate. They will be provided with a separate patient information sheet which explains the difference between the service evaluation and the study. Retrospective consent will be sought to use this information as part of this study.

7.0 Trial Procedures

7.1 Recruitment

All eligible patients will be identified at the Leeds Breast diagnostic MDT meetings and through clinics. Those planned for a mastectomy and implant based reconstruction are offered the option of completing the BREAST-Q as part of routine care. The direct clinical team will discuss this with the patient and this will not impact on routine care of decision making for either pre- or sub-pectoral implant based reconstruction (i.e. non-randomised). All patients deemed eligible will be offered the study patient information sheet and given a minimum of 24 hours to consider the study. As common practice is for surgery to be 2-3 weeks after the clinic appointment, there will be sufficient time for the patient to consider the information and ask any questions they may have about participation.

7.2 Informed Consent

The participant must personally sign and date the latest approved version of the Informed Consent form before any study specific procedures are performed. It is the responsibility of the Chief Investigator (or designee as listed on the Site Responsibilities Form) to obtain written informed consent in compliance with national requirements from each patient prior to entry into the study. On the day of surgery, the clinical team will confirm if the patient wishes to participate and if yes, will arrange for consent to be taken. Written informed consent will be taken by an appropriately trained member of the team and may include experienced research nurses or trials assistants, as per the delegation log. This is in accordance with Good Clinical Practice (GCP) guidelines and will have been documented and approved by the Chief Investigator on the delegation log. Patients will be reminded that participation is voluntary and that they can withdraw at any time point without this affecting their care. This process will be clearly documented in the patients' medical notes.

A copy of the signed Informed Consent will be given to the participant. The original signed form will be retained in the trial site file and a copy will be placed in the patient's notes.

There will be two study PIS's; one for prospective patients and one for retrospective patients who participated in the local service evaluation and have already completed BREAST-Q questionnaires. There will be two ICFs for the study, one for those entering as prospective patients who have not yet had their surgery and a separate ICF for those who participated in the local service evaluation.

On consent, all participants will be allocated an anonymised sequential trial identification number which will be used on all trial data collection.

7.2.1 Patients who withdraw consent

Patients are free to withdraw from the study at any time.

7.3 Baseline Assessments

Once written informed consent is obtained, participants will be asked to complete the baseline questionnaire. Clinical data will be obtained from medical notes by the clinician and/or research team and will include (but not limited to) gender, age, diagnostic details, co-morbidities, smoking status, previous surgical and planned treatments.

Timepoint 0

After consent but prior to surgery

Following written informed consent and prior to the planned surgery, the baseline BREAST-Q questionnaire will be completed by every patient.

The following data items will be collected during the study:

- Reason for surgery (cancer or risk reduction)
- Uni or Bilateral surgery
- Type of mastectomy (skin and nipple preserving or nipple sacrificing, skin reducing)
- Pre- or sub-pectoral reconstruction
- Any axillary surgery
- Breast implant size
- Details of any anaesthetic block used (to reduce post-operative pain)
- Any additional cancer treatments (e.g. chemotherapy, radiotherapy)
- Any complications (e.g. haematoma, infection)
- Unplanned hospital re-admission
- Unplanned further surgery
- Implant loss at 3 months due to infection
- Expectation of pain after surgery
- Expectation of appearance after surgery
- Expectation of breast symmetry
- Expectation of change in sensation
- Satisfaction of breast shape and implant
- Psychosocial well-being
- Physical well-being related to chest
- Satisfaction with the information and care provided by the clinical team
- Sociodemographic information

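### Section 7.3 records which plane was used but does not require the reason for it, who drove the choice, or height and weight, so selection into the two groups may not be examinable

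*Protocol*

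**What the plan says.** Section 5.1 describes a non-randomised cohort, and Section 7.1 leaves the choice of plane to routine care. The background section, before Section 4, reports that about equal numbers choose each plane and adds: "However, it is unclear how much of this decision making is influenced by the patient or the surgeon".

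Section 7.3 gives a list, expressly open-ended, of the clinical data to be taken from the notes: "gender, age, diagnostic details, co-morbidities, smoking status, previous surgical and planned treatments". Its list of study items includes:

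- the exposure, "Pre- or sub-pectoral reconstruction";
- one item giving a reason, "Reason for surgery (cancer or risk reduction", which is the reason for the mastectomy and not for the plane;
- one item related to size, "Breast implant size".

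Neither Section 7.3 nor the process-of-care list in Section 5.2 names the reason for the plane, who chose it, or height, weight or BMI.

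For the analysis, Section 8.2 describes a simple comparison of BREAST-Q scores between the two groups, without mentioning adjustment.

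**The concern.** Section 4 asks whether the technique influences patient-perceived outcomes, and the background says a difference would matter for counselling future patients. That is a causal question put to self-selected groups, so the answer depends on knowing how the groups came to differ.

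The Protocol identifies one unknown in that process, the balance between patient and surgeon influence, and then sets no item to capture it. If women who differ in build, tissue or preference tend towards one plane, and those traits also affect satisfaction or pain, part of the observed difference will be credited to the plane when it belongs to the selection. An analysis plan can add covariates, but it cannot supply a judgement that nobody wrote down at the time.

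**Working it through.** **1. Items needed against items named (Sections 5.2 and 7.3)**

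| Needed to examine selection | Named? | Nearest named item |
|---|---|---|
| Plane used | Yes | – |
| Main reason for the plane | No | Reason for mastectomy |
| Who drove the choice | No | None |
| Height and weight, or BMI | No | Implant size, co-morbidities (weak proxies) |
| Age, smoking, laterality, mastectomy type, other cancer treatment, expectations, sociodemographics | Yes | – |

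**2. Can the missing items be recovered later?** Height and weight may be, because the Section 7.3 list is open and Section 9.1 makes hospital records source data. The main reason for the plane is a judgement made at the time, and nothing in the Protocol requires it to be written in the notes. It probably cannot be rebuilt reliably.

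**3. Group size.** The background gives about 100 immediate reconstructions a year, 60% of them implant based: 100 × 0.60 = 60 a year. This reproduces the estimate in Section 8, and the planned minimum in Section 8.1 is also 60. An equal split gives about 30 per group.

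**4. Illustration of size.** The Protocol gives no standard deviation, effect or prevalence, so every input here except the 30 per group is assumed.

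For an unrecorded yes/no trait, bias in the unadjusted mean difference = effect of the trait × difference in its prevalence between groups.

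- Prevalence 50% v 20%, effect 6 points: 6 × 0.30 = 1.8 points.
- Prevalence 60% v 20%, effect 10 points: 10 × 0.40 = 4.0 points.
- Prevalence 40% v 30%, effect 6 to 10 points: 6 × 0.10 = 0.6 to 10 × 0.10 = 1.0 points.

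Standard error of the difference = SD × √(2/30):

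- SD 15: 15 × 0.258 = 3.9 points.
- SD 25: 25 × 0.258 = 6.5 points.

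The bias therefore runs from 0.6/6.5 ≈ 0.1 to 4.0/3.9 ≈ 1.0 standard errors.

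**5. Wider grid.** Take effects of 5 to 15 points, prevalence differences of 20 to 40 percentage points, and no true effect of technique. The spurious difference is 5 × 0.20 = 1 to 15 × 0.40 = 6 points. With b the bias, a nominal 5% two-sided test rejects with probability Φ(b/SE − 1.96) + Φ(−b/SE − 1.96):

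- b = 1, SD 25: 5.3%.
- b = 4, SD 20: 12.1%.
- b = 6, SD 15: 34.1%.

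So the effect ranges from negligible to serious, and nothing in the documents shows where this study lies.

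**The case against.** The strongest reply has four parts.

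- **The list is open and drawn from the notes.** This stands for body size: the items are not named, which is different from saying they will not be recorded. It carries little weight for the reason for the plane, since an open list obliges nobody to collect a given item.
- **Other confounders are named.** This also stands. Age, smoking, co-morbidities, reason for surgery, laterality and pre-operative expectations could all be used in adjustment, and a separate analysis plan may say so. None of them records why the plane was chosen.
- **The assumed bias is mostly below one standard error.** True. The illustration does not show that a conclusion would change.
- **The remedy is imperfect.** True. BMI is only a proxy for tissue cover, and women who choose by preference still differ from one another.

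A reader might go further and infer from Table 1 that tissue cover drives the choice of plane. The table does not say this. Its pre-pectoral column lists "Thin tissue coverage over the implant. This may increase the risk of rippling", and its sub-pectoral column lists additional cover, so cover over the implant appears as a consequence of the plane. That a woman's own tissue guides the choice is plausible, but no section states it. Nor does the background say that the basis of the decision is wholly unknown: what it calls unclear is the share of influence between patient and surgeon.

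**Conclusion.** The gap is real but limited. The Protocol does not require the reason for the plane, the decision-maker, or height and weight in a non-randomised comparison whose stated analysis is a simple one. Confounding by indication on these factors may therefore not be examinable. The reason for the plane is the more pressing item, because it probably cannot be recovered later.

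The size is unknown. The figures of 0.6 to 4.0 points, and 1 to 6 points on the wider grid, rest on assumed effects and prevalences; the standard errors and rejection rates also rest on an assumed SD of 15 to 25 with 30 women per group.

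It would be too strong to conclude that confounding is beyond any adjustment as the plan stands, since several confounders are named and body size may be retrievable. It would be equally wrong to expect the added items to eliminate it. This is an inexpensive improvement that should be made, and not a defect that invalidates the study.

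**What to change.** Add to Section 7.3, as required items:

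1. One field, completed by the operating team before or at surgery, giving the main reason for the plane: patient preference, surgeon advice, tissue or flap quality, or other.
2. Height and weight from the routine pre-operative record.

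In Section 8.2 or the analysis plan, tabulate both by group, include BMI as a covariate in the technique comparison, and report a sensitivity analysis restricted to women whose plane was chosen by patient preference, labelled exploratory.

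For service-evaluation participants (Section 6.4), who have already completed questionnaires, the reason would be recorded retrospectively, possibly with the outcome known. Flag those entries.

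The cost is one form field, two routine measurements and a short addition to the analysis text, with no extra visit or test. The limits should be stated:

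- the reason is a judgement, and BMI is only a proxy for tissue cover;
- about 60 patients support few covariates;
- the restricted subset will be small. If half the women qualified (an assumption), 15 per group would give a standard error of SD × √(2/15), or 15 × 0.365 = 5.5 to 25 × 0.365 = 9.1 points.

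### The operating surgeon is not among the listed data items, although the protocol names surgeon preference as one of two determinants of technique

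*Protocol*

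**What the plan says.** **How technique is chosen.** Section 4 (Aims) says that, without evidence or guidelines, "the type of operation undertaken usually comes down to surgeon or patient preference". The background section reports that at this centre an "equal proportion of patients opt for pre- versus sub-pectoral implant based IBR", and adds that "it is unclear how much of this decision making is influenced by the patient or the surgeon". Section 5.1 describes "A prospective non-randomised longitudinal cohort study", and section 7.1 says the study will not affect the choice of plane.

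**What is recorded.** Section 7.3 opens its list with "The following data items will be collected during the study". The 21 items include "Pre- or sub-pectoral reconstruction", mastectomy type, axillary surgery, implant size, anaesthetic block and complications. None is the operating surgeon. Clinical data taken from the notes "will include (but not limited to) gender, age, diagnostic details, co-morbidities, smoking status, previous surgical and planned treatments". Section 5.2 gives, as examples of process measures, "anaesthetic blocks used, number of hospital contacts, unplanned admissions, clinic appointments, phone calls with hospital staff". The surgeon is not mentioned there, nor in sections 8.2 or 8.4.

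**What is compared.** Section 8.2 plans a simple statistical comparison of BREAST-Q scores between the two planes and names no adjustment for surgeon.

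**The concern.** The protocol identifies a possible driver of the exposure and then does not provide for recording it. A surgeon can plausibly affect appearance, pain and function, which are the three objectives in section 4. If surgeons also differ in how often they use each plane, the surgeon is linked to both exposure and outcome, and no patient-level item on the list stands in for it.

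The background section says that a difference in patient-reported outcomes would bear on how future patients are counselled. A difference between surgeons' patients could then be reported, and used in counselling, as a difference between techniques.

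This belongs in the protocol because it concerns data capture. An analysis plan can choose how to adjust, but not for a variable that was never collected.

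**Working it through.** **The plan's own figure.** The background gives about 100 immediate reconstructions a year, 60% of them implant-based: 0.60 × 100 = 60 a year. This reproduces the availability stated in section 8. The point does not depend on it, except that 60 is also the planned minimum sample (section 8.1).

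**Document check.** The places that list data or analyses (sections 5.2, 7.3, 8.2 and 8.4) contain no operator item. The plane is listed; the person who operated is not.

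**Size of bias in points.** The documents give no surgeon numbers, so these inputs are assumptions: two surgeons, A and B, of equal volume; 30 patients per technique, in line with the roughly equal split in the background; no true technique effect; and patients of A and B differing by D = 8 points on the 0–100 scale for reasons unrelated to plane. Let p_A and p_B be the shares of each surgeon's cases done pre-pectorally, with p_A + p_B = 1. Then A's share is p_A of the pre-pectoral group and 1 − p_A = p_B of the sub-pectoral group, so

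spurious difference = (p_A − p_B) × D.

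- 50/50: (0.5 − 0.5) × 8 = 0
- 60/40: (0.6 − 0.4) × 8 = 1.6
- 80/20: (0.8 − 0.2) × 8 = 4.8

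The result is proportional to D, so halving D halves each figure.

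**The same in SD units.** The protocol gives no SD, so this is a separate illustration. Write d = p_A − p_B and let g be the surgeon effect in SDs. Bias = d × g. With 30 per group the standard error is √(2/30) = 0.258 SD. The chance of a false positive at two-sided 5% (normal approximation) is 1 − Φ(1.96 − bias/0.258) + Φ(−1.96 − bias/0.258). If surgeon is recorded and adjusted for, the variance is multiplied by 1/(1 − d²), so the effective sample is 60 × (1 − d²).

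| Split | d | Bias, g = 0.25 / 0.5 / 0.75 | False-positive rate | Effective N after adjustment |
|---|---|---|---|---|
| 50/50 | 0 | 0 / 0 / 0 SD | 5% / 5% / 5% | 60 |
| 60/40 | 0.2 | 0.05 / 0.10 / 0.15 SD | 5.4% / 6.7% / 8.9% | 60 × 0.96 = 57.6 |
| 80/20 | 0.6 | 0.15 / 0.30 / 0.45 SD | 8.9% / 21.3% / 41.4% | 60 × 0.64 = 38.4 |

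If each surgeon uses only one plane, d = 1, the effective sample is zero and no adjustment is possible.

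**The case against.** The strongest reply is that nothing in the protocol prevents collection. The clinical data taken from the notes are open-ended ("will include (but not limited to) gender, age, diagnostic details, co-morbidities, smoking status, previous surgical and planned treatments"), section 5.2 gives examples only, and the operation can be traced through the records. This stands, and it limits the point to a failure to pre-specify the item. It does not remove it: permission to collect does not ensure that the field is captured for every participant, including the service-evaluation patients of section 6.4 who enter by retrospective consent.

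A second reply is that the problem may not exist. There may be one surgeon, or all surgeons may use both planes in similar proportions, and then the bias is near zero. This also stands. The documents do not settle it, and a technique-by-surgeon table would.

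A third reply is that 60 patients are too few to adjust. At an 80/20 split the effective sample falls to 38.4, so the cost can be substantial. That argues for showing adjustment as a sensitivity analysis. It does not argue against recording the surgeon.

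A reader might also infer more than the text supports:

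- *That the surgeon could not be recovered later because the data are anonymised.* Sections 9 and 9.3 remove patient identifiers and say nothing against a surgeon code, and section 9.1 requires linkage between case report forms and hospital records.
- *That surgeon preference determines technique.* Section 4 names surgeon or patient preference, and the background calls the surgeon's share unclear.
- *That several operators, including trainees, make this a main route of confounding.* The protocol says only that the unit is a fellowship centre. It gives no operator numbers, grades or technique mix.
- *That the study ought to establish who drives the choice.* This is background and not one of the three objectives. The reason for choosing a plane is a judgement that the documents do not show to be recorded in the notes.

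**Conclusion.** The point holds in a limited form. Surgeon preference is one of two stated determinants of technique, the planned comparison is a simple one in a non-randomised cohort, and the operating surgeon is not a listed item. Followed as listed, the dataset could not distinguish surgeon differences from technique differences, although the item remains obtainable.

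The size of any bias is unknown. Under the assumptions shown it runs from zero at an equal split to 1.6 points at 60/40 and 4.8 points at 80/20. The 8-point surgeon difference, the two equal-volume surgeons and the splits are all illustrative. The figures show that the concentration of technique by surgeon matters; they are not evidence that this centre has such a concentration. The change should be made because it is cheap and cannot be replaced by a choice of analysis.

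**What to change.** - Add *Operating surgeon (coded)* to the section 7.3 list for all participants, including service-evaluation patients, taken from the operation note.
- Report a table of technique by surgeon code.
- Where surgeons used both planes, show a surgeon-adjusted comparison as a sensitivity analysis beside the simple one.
- Where surgeon and technique largely coincide, state in the report that the two effects cannot be separated.

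The cost is one extra coded field, with no additional visit or questionnaire. The adjusted estimate will be less precise than the simple one in a sample of 60, and the loss grows as technique becomes more concentrated by surgeon. Recording the surgeon allows separation only if at least some surgeons perform both techniques.
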